4 STUDY DESIGN

4.1 OVERALL DESIGN

- The study is a multicenter, randomized superiority trial of **standard of care** therapies for **severe aortic stenosis** (AS) in patients with a bicuspid aortic valve (BAV). Namely, the therapies to which patients will be randomized will be **transcatheter** aortic valve replacement (TAVR) or **surgical** aortic valve replacement (SAVR), in patients deemed clinically suitable for both **following patient selection committee review**.
- The null hypothesis is that there is **no difference between TAVR and SAVR** in relation to the hierarchical primary composite endpoint. The alternative hypothesis is that **TAVR differs from SAVR**. The test for superiority is two-sided, such that SAVR or TAVR superiority could be demonstrated.
- Patients deemed suitable for randomization at the individual level by a local heart team will be **affirmed by the patient selection committee**.
- For the patient to be suitable for randomization, there must be relative equipoise, defined as follows: the TAVR and SAVR risk strata, as adjudicated by the committee, must not deviate by more than one risk

stratum. For instance, a low SAVR risk patient cannot be randomized if the TAVR risk is deemed high, and vice versa. However, an intermediate SAVR risk patient could be randomized if the TAVR risk is low or high and vice versa.

- **Representativeness of Patient Population.** From the outset, we will require that at least 35% of enrolled patients are women and at least 20% are from racial or ethnic minority groups. We have chosen initial sites that already treat a high proportion of these patients, and we are partnering with Heart Valve Voice and Heart Valve Surgery (patient advocacy organizations) to provide culturally tailored outreach material, multilingual e-consent, and community-oriented communication materials that will facilitate targeted recruitment. Enrollment metrics for sex and race will be periodically reviewed. If any site drifts more than five percentage points below either target for 3 consecutive months, the study team will deploy additional recruitment tools (e.g., transportation vouchers) and, if necessary, activate “reserve” sites whose historical case-mix exceeds the diversity thresholds. These steps will ensure that all key demographic subgroups reach the numbers required for ≥ 80 percent power in the planned interaction tests. Many per protocol questionnaires such as KCCQ are available in multiple languages and which will be used in the patients native tongue as necessary; some patient centered questionnaires (such as QOR) have not been translated or validated for languages other than English, in which case an interpreter will be used, if available at the treating center.
- Patients will be randomized 1:1 to TAVR or SAVR using permuted block randomization with varying block size. We will require **$\geq 35\%$ to be female**. To **ensure a balance between treatment arms**, randomization will be **stratified by (1) sex** and (2) low or intermediate/high SAVR (clinical) risk, (3) planned TAVR type (in the event of randomization to TAVR). Randomization will be adaptive to maintain balance in study arm allocation within each site. This study is open-label; patients, treating clinicians, and site staff will not be blinded to treatment assignment.
- All randomized patients will be assessed peri- and post-procedure, at discharge, 30 days, 1 year, and then annually for up to 10 years post-procedure. The visits at 30 days and 1 yr are to be in-person at investigational site. Visits at years 2 -10 can be virtual or in-person at investigational site. Labs, ECG and Echo may be done locally.
- Patients deemed **unsuitable for randomization** but who **meet inclusion criteria** and ultimately undergo SAVR or TAVR are of interest and will be entered into the SAVR and TAVR registry cohorts. Operational details, follow-up procedures, and analytic plans for these parallel SAVR and TAVR registry cohorts are outside the scope of the present randomized trial protocol, as the registries will be supported through separate funding and described in separate registry-specific documents.

[figure not shown]

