9.4 STATISTICAL ANALYSES

9.4.1 General Approach

Under the stated assumptions, we used 10,000 simulated trials to determine that 1020 patients with complete 3-year data achieves 85.3% power for a two-sided Finkelstein-Schoenfeld at a 5% significance level. Simulations randomly generated time-to-event data for each clinical event using an exponential distribution, with the rates for each component tailored so that the distribution of the most severe outcome within each patient followed the distribution given in Table 2. KCCQ outcomes were randomly generated from a binomial distribution. To allow for a small number of crossovers, loss-to-follow up (estimated at around an eighth or 12.5% of patients, in line with PARTNER trials), we propose to recruit a total of **1,200 randomized patients, 600 in each arm**. This sample size yields >95% power for the analysis of the key secondary outcome (a hierarchical composite of death and time-averaged KCCQ score) if SAVR improves the average KCCQ score by 3 points under the assumption that the standard deviation of an individual KCCQ measurement is 20. **Our key secondary outcome** is similar to the primary endpoint of the PCORI-funded RECHARGE study, which will study a hierarchical composite of death and SF-12 quality of life assessment, using the win ratio(5). Such a magnitude of improvement in KCCQ is regarded as clinically meaningful and, in context, is similar to that seen in novel heart failure drugs that have impacted survival and quality of life(6).

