AEs will be summarized as the number and percentage of participants experiencing at least one event, overall and by study arm. In addition, exposure-adjusted incidence rates (events per 100 patient-years) will be presented when appropriate to account for differences in exposure duration. For each AE the following will be recorded: seriousness, start date, stop date, severity, relationship, expectedness, and outcome. Adverse events leading to premature discontinuation from the study intervention and serious treatment-emergent AEs will be presented in a listing.

9.4.6 **Sub-Group Analyses**

We recognize that any overall treatment effect may not apply equally to all patients, so the use of subgroup analyses to explore such potential heterogeneity is of enormous value. Thus, we will pre-define key patient characteristics that will form the basis for subgroup analyses and their associated tests of heterogeneity. We have the relevant statistical expertise on this topic (e.g. Pocock et al, *Statistical Controversies in Reporting of Clinical Trials*, JACC 2015;66:2648-62(7)). While enquiries into heterogeneity of effects are useful, it is widely known that they have reduced statistical power. For instance, for the primary outcome we have 85% power under the assumption that the relative risk is 0.75. If such an effect truly splits into relative risks of 0.5 and 1.0 respectively in a subgroup analysis (an all-or-nothing interaction) this would be detectable with power slightly less than 60%. We will therefore also perform subgroup analyses of time-averaged KCCQ assuming a standard deviation of 14.5 for which we have adequate power to detect **heterogeneity of treatment effect**.

Sex: We will have 82% power to detect heterogeneity of the treatment effect between men and women (using a test of interaction with 5% significance) if the difference in the effect of time-averaged KCCQ between men and women is 5 units. This power is calculated for the mandated minimum 35% of women, and will be greater if the proportion of women actually recruited is higher.

Age: We will perform subgroup analyses according to age (<65 vs. ≥65 years). If the difference in the effect of TAVR vs. SAVR on time-averaged KCCQ between younger and older patients is 5 units, we will have 85% power to detect heterogeneity of treatment effect at a 5% significance level (alpha), assuming an approximately 50/50 split between age groups.

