9.4.7 Exploratory Analyses

Other prespecified **exploratory** subgroups of interest will be **pre-specified planned TAVR type, pre-specified planned coronary revascularization**, presence of **aortopathy** (ascending aorta maximal dimension ≥ 40 mm). The win ratio comparing TAVR to SAVR will be calculated separately within each subgroup and formal tests of interaction subgroups will be used to ascertain whether the treatment effect differs between subgroups based on a Z-test calculated as the difference between stratified log win ratios. (11). For subgroup analyses using time-averaged KCCQ score, formal statistical tests of interaction will be used to compare whether the treatment effect on time-averaged KCCQ scores (estimated from linear models) varies according to patient characteristics.

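### Section 4.1 assures at least 80% interaction power for all key demographic subgroups, but the protocol plans no race/ethnicity interaction test and gives no effect size for one

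*Protocol*

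**What the plan says.** Section 4.1 (paragraph on representativeness) requires that "at least 35% of enrolled patients are women and at least 20% are from racial or ethnic minority groups". The remedial steps apply to both minimums: "If any site drifts more than five percentage points below either target for 3 consecutive months", the study team adds recruitment tools and, if needed, activates further sites. The paragraph then gives the power assurance: "These steps will ensure that all key demographic subgroups reach the numbers required for ≥ 80 percent power in the planned interaction tests". That sentence names neither the outcome nor the tests it means.

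The tests are in Sections 9.4.6 and 9.4.7:

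- **Section 9.4.6, time-averaged KCCQ, standard deviation 14.5.** Sex: 82% power at 35% women, "if the difference in the effect of time-averaged KCCQ between men and women is 5 units". Age (<65 vs ≥65): 85% at 5 units with an even split. TAVR risk: 87% at 6 units with 25% intermediate/high. SAVR risk: 92% at 6 units with 33% intermediate/high.
- **Section 9.4.6, primary outcome.** Power to detect an all-or-nothing interaction (relative risks 0.5 and 1.0) is put at just under 60%.
- **Section 9.4.7, exploratory subgroups.** Planned TAVR type, planned coronary revascularization, and aortopathy ("ascending aorta maximal dimension ≥ 40 mm"), with win-ratio interaction tests as well as tests on time-averaged KCCQ.

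Race/ethnicity appears in neither section.

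**The concern.** The two groups that the Section 4.1 steps protect are women and racial or ethnic minority patients. The power sentence that closes the paragraph therefore reads as covering both. For sex there is a listed test, an effect size and a printed power. For race/ethnicity there is none of these.

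Sections 2.2 and 2.3.2 name the scarcity of data in women and ethnic minorities as a gap and say that the trial will give more insight into their outcomes. As written, the 20% minimum is linked to a power property that the protocol does not derive, and no treatment-effect comparison by race/ethnicity is listed. A reader of a later race/ethnicity comparison could cite Section 4.1 as evidence that it had at least 80% power.

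**Working it through.** **Inputs**

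- Total N: "1,200 randomized patients, 600 in each arm" (Section 9.4.1).
- Allocation: "Patients will be randomized 1:1 to TAVR or SAVR" (Section 4.1).
- SD of time-averaged KCCQ: 14.5 (Section 9.4.6).
- Test level: 5% (Section 9.4.6), taken as two-sided, z = 1.96.
- Interaction size d: 5 units for sex and age, 6 units for the two risk strata (Section 9.4.6). None is stated for race/ethnicity.
- Smaller-subgroup share p: 20% minimum for minority patients (Section 4.1).
- Allowance: 12.5% for crossovers and loss to follow-up together (Section 9.4.1). If all of it were lost, N = 1200 × 0.875 = 1050.

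**Formula** (two subgroups, 1:1 within each)

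SE = 2 × SD × √[1/(pN) + 1/((1−p)N)]; power = Φ(d/SE − 1.96)

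**Step 1. Reproduce the protocol's figures at N = 1200**

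| Test | p | d | SE | Computed | Protocol |
|---|---|---|---|---|---|
| Sex | 0.35 | 5 | 29 × √(1/420 + 1/780) = 1.755 | 81.3% | 82% |
| Age | 0.50 | 5 | 29 × √(1/600 + 1/600) = 1.674 | 84.8% | 85% |
| TAVR risk | 0.25 | 6 | 29 × √(1/300 + 1/900) = 1.933 | 87.4% | 87% |
| SAVR risk | 0.33 | 6 | 29 × √(1/396 + 1/804) = 1.780 | 92.1% | 92% |

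All four agree within one percentage point. A noncentral-t calculation gives 81.2%, 84.7%, 87.3% and 92.0%. At N = 1050 the four become 76.0%, 79.8%, 82.7% and 88.4%, which do not match. The printed powers therefore count all 1200 patients as complete.

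**Step 2. Apply the same method to a 20% share**

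- N = 1200: SE = 29 × √(1/240 + 1/960) = 2.093.
- N = 1050: SE = 29 × √(1/210 + 1/840) = 2.237.

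| d | N = 1200 | N = 1050 |
|---|---|---|
| 5 units | Φ(2.389 − 1.96) = 66.6% | Φ(2.235 − 1.96) = 60.8% |
| 6 units | Φ(2.867 − 1.96) = 81.8% | Φ(2.682 − 1.96) = 76.5% |

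**Step 3. What 80% power would need**

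- At a 20% share, the detectable difference is (1.96 + 0.842) × SE: about 5.9 units at N = 1200 and 6.3 units at N = 1050.
- At 5 units and N = 1200, the minority share would have to be about 33%.
- At 5 units and a 20% share, about 1650 patients would be needed.

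**Step 4. Which outcome the sentence can refer to**

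The primary-outcome interaction power of just under 60% is the protocol's own figure and was not re-derived. It rules out an 80% assurance for win-ratio interaction tests. The Section 4.1 sentence can be true only for time-averaged KCCQ, which it does not say.

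**The case against.** **No race/ethnicity test is planned, so the sentence claims nothing about one.** Read literally, the planned demographic tests are sex and age, and both printed powers exceed 80%. The second part is correct: no printed figure is wrong. But the steps named in the sentence act on the sex and race/ethnicity minimums, and it speaks of all key demographic subgroups. A literal reading saves it only by dropping one of the two groups it was written about.

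**The 5-unit difference is borrowed.** This stands. A reader might infer that a 20% share cannot reach 80% power even with 1200 complete patients. The protocol does not support that: it states no race/ethnicity interaction size, and at the 6 units it uses for its 25% and 33% splits the power is 81.8%. The shortfall holds at 5 units, the value used for both demographic tests.

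**The subgroup list may not be closed.** Section 9.4.6 speaks of subgroups still to be pre-defined, and the SAP, which is not shown, may add race/ethnicity. Absence from the list alone would be no finding. What remains is that Section 4.1 already asserts a power result for planned tests, with no calculation behind it for this group.

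**1050 may not be the analysed number.** This also stands. The 12.5% covers crossovers as well as loss, and Section 9.4.8 imputes missing KCCQ for the time average. The 1050 figures are a lower scenario.

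**The site trigger does not imply a 15% minority share.** A reader might take the five-point tolerance as permitting 15% across the trial. It is a site-level signal for action, so no trial-wide power should be computed from it.

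**The targets are about representativeness.** Section 10.1.6.6 presents them as equity goals, and they need no power justification. That is fair, and it is a reason to remove an unsupported one.

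**Conclusion.** The point holds as an unsupported assurance, not as an error in a printed power. For race/ethnicity the Section 4.1 sentence has no listed test, interaction size or calculation behind it.

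On the protocol's own inputs, whether the 20% minimum delivers 80% depends on the difference assumed: it does not at 5 units, and it does at 6 units only if the analysis keeps close to all 1200 patients. This assumes SD 14.5 in both subgroups, a two-sided 5% test, balanced arms within subgroups and exactly the minimum share; a higher share would raise the power. For sex and age the sentence is right on time-averaged KCCQ with 1200 patients. For the win ratio it conflicts with Section 9.4.6.

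**What to change.** 1. **Section 4.1.** Limit the 80% statement to the sex and age interaction tests on time-averaged KCCQ, at 5 units with 1200 patients. Then state what the minority minimum delivers, for example: *At a 20% share, a race/ethnicity interaction on time-averaged KCCQ has about 67% power at 5 units and 82% at 6 units with 1200 complete patients (about 61% and 76% with 1050); 80% power needs a difference of about 5.9 units with 1200 complete patients.*
2. **Section 9.4.6.** Add race/ethnicity (minority vs non-minority) as a subgroup, reported as an interaction estimate with confidence interval on time-averaged KCCQ, and labelled as not powered to 80% at 5 units.

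The cost is a less favourable stated power and one more subgroup test. Demographics are already collected at baseline, so no extra patients or data are needed, and the enrolment targets can stay as they are.

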4.2 SCIENTIFIC RATIONALE FOR STUDY DESIGN

While TAVR has an extensive randomized evidence base in severe aortic stenosis, the pivotal trials that established its use across risk categories systematically excluded patients with bicuspid anatomy, leaving contemporary treatment decisions in BAV to be guided largely by observational data, selective registries, and an underpowered randomized trial, despite BAV being common and disproportionately affecting younger patients. In this setting, A pragmatic randomized comparison of two standard-of-care options (TAVR vs SAVR) is the best way to provide unbiased comparative effectiveness evidence. But BAV anatomy varies widely, and TAVR risk may differ from SAVR risk within the same “surgical risk” group. For this reason, the trial uses **imaging-guided selection** and prespecified risk strata to ensure clinical equipoise (TAVR and SAVR strata differ by no more than one level) and to avoid randomizing patients with clearly unfavorable anatomy for one approach. The primary endpoint uses a hierarchical win ratio because it incorporates both the timing and occurrence of events and uses all available follow-up rather than a single time point. This is especially important in younger BAV patients, where durability and later reintervention matter. The composite therefore includes valve reintervention and unfavorable KCCQ to capture both long-term outcomes and patient-centered health status.

4.3 END OF STUDY DEFINITION

A patient is considered to have completed participation in the study if he or she has completed all phases of the study including the last visit or the last scheduled procedure shown in the Schedule of Activities (SoA), Section 1.3, or has withdrawn from the study. The determination of loss to follow-up will not be made until the end of the study. The end of the study is defined as 10 years (+ or - 45 days) following the randomization of the 1200th patient.

5 STUDY POPULATION

The study population consists of patients with severe symptomatic AS presenting for TAVR or SAVR under standard of care treatment. Enrollment of patients in the randomized cohort of the study will be contingent on the Patient Selection Committee (PSC) review of the suitability for randomization, including an evaluation of operative (SAVR) risk presented by the treating site and an imaging-based evaluation of TAVR risk based on CT Corelab evaluation of uploaded CT data. For clarity, although the PCORI funding is only intended to support patients randomized in the study, all BELIEVERS trial consented patients who meet the broad inclusion criteria, including those deemed unsuitable for randomization but ultimately undergo SAVR or TAVR are of interest and will be entered into the SAVR and TAVR registry cohorts.

5.1 INCLUSION CRITERIA

In order to be eligible to participate in this study, an individual must meet all of the following criteria:

1. 50 years of age or older at time of consent;
2. Severe AS (see section 5.1.1) deemed suitable for a bioprosthesis by a local heart team (unsuitable or patient declined a mechanical valve or Ross procedure, following demonstration of **evidence-based shared decision making with a validated decision-aid(1)**);
3. Gated contrast CT available and suitable for core laboratory analysis;
4. BAV anatomy confirmed by CT core laboratory analysis;

5.1.1 Qualifying criteria for severe AS (site reported)

A. High-gradient severe AS (any one):

- Peak aortic jet velocity (Vmax) \geq 4.0 m/s, or
- Mean transvalvular gradient \geq 40 mmHg, or
- Aortic valve area (AVA) \leq 1.0 cm² (or indexed AVA \leq 0.6 cm²/m²), consistent with severe AS.

B. Low-flow, low-gradient severe AS (suspected)

If $AVA \leq 1.0 \text{ cm}^2$ but $V_{max} < 4.0 \text{ m/s}$ and mean gradient $< 40 \text{ mmHg}$, severe AS must be confirmed by at least one of the following, per site standard practice and documented in source records:

- Dobutamine stress echocardiography showing severe AS at peak stress (e.g., mean gradient $\geq 40 \text{ mmHg}$ with $AVA \leq 1.0 \text{ cm}^2$), or
- CT aortic valve calcium scoring supportive of severe AS (sex-specific thresholds per local standard), or
- Additional Heart Team-supported evidence consistent with true severe AS (e.g., consistent Doppler findings and clinical presentation).

C. Qualifying echo timing

The qualifying TTE should be performed within 90 days prior to randomization.

5.2 EXCLUSION CRITERIA

An individual who meets any of the following criteria will be excluded from randomization in this study. However, a Patient who fulfills the inclusion criteria but presents with any of the exclusion criteria would be enrolled in the registry (unfunded by PCORI).

1. Recent cardiovascular intervention within 30 days prior to randomization.
2. Presence of an existing TAVR or SAVR device
3. Pregnancy or lactation
4. Extreme or prohibitive TAVR or SAVR risk, adjudicated by the PSC review.
5. Active enrollment in another investigational study
6. Disproportionate TAVR vs SAVR risk, as adjudicated by the patient selection committee
7. Associated aortopathy ($AA \geq 45 \text{ mm}$ by maximal cross-sectional dimension, as confirmed by CT core laboratory analysis, or $AA < 45 \text{ mm}$ but site plan for surgery of the aorta in the event of randomization to surgery)
8. Site plan for treatment of concomitant non-coronary cardiovascular disease in the event of randomization to surgery (for instance, concomitant valve surgery, septal defect or coarctation repair, aorta or root replacement or repair)
9. In the presence of coronary artery disease deemed necessary for revascularization in the event of randomization to SAVR or TAVR, Syntax score ≥ 32 or deemed unsuitable for PCI, or deemed unsuitable for coronary artery bypass grafting (CABG).
10. Plan to use any device other than commercially approved Edwards balloon expandable or Medtronic self-expanding TAVR.
11. Leukopenia ($WBC < 3000 \text{ cells}/\mu\text{L}$), anemia ($Hgb < 8 \text{ g/dL}$), Thrombocytopenia ($Plt < 50,000 \text{ cells}/\mu\text{L}$) on latest available labs within 30 days prior to randomization.
12. Hemodynamic or respiratory instability requiring inotropic support, mechanical ventilation, or mechanical heart assistance within 30 days prior to randomization
13. $LVEF < 25\%$ within 90 days prior to randomization.
14. Stroke or transient ischemic attack (TIA) within 90 days prior to randomization
15. Renal insufficiency ($eGFR < 30 \text{ ml/min}$ per the Cockcroft-Gault formula)
16. Severe lung disease ($FEV1 < 50\%$ predicted), unresolved prior to randomization.
17. History of liver disease defined as MELD Score ≥ 10 or Child-Pugh Class B or C.
18. Unable to complete the KCCQ due cognitive impairment or other medical condition.

